2.2 Analysis sets

Full Analysis Set

The **Full Analysis Set** (FAS) comprises all patients to whom study treatment has been assigned and who received at least one dose of pazopanib.

Safety

The **Safety set** includes all patients who received at least one dose of pazopanib. The safety set and the FAS are the same for this single arm phase II study.

Other

Not applicable.

Pharmacokinetic analysis set (PAS)

Not applicable.

Patient Classification:

Patients may be excluded from the analysis populations defined above based on the protocol deviations entered in the database and/or on specific patient classification rules defined in [Table 2-3](#).

Table 2-2 Patient classification based on protocol deviations and non-protocol deviation criteria

Analysis set	Protocol deviations leading to exclusion	Non protocol deviation leading to exclusion
FAS	No written informed consent	No dose of study medication
Safety set	No written informed consent	No dose of study medication

Withdrawal of Informed Consent

Any data collected in the clinical database after a patient withdraws informed consent from all further participation in the trial, will not be included in the analysis. The date on which a patient withdraws full consent is recorded in the eCRF.

2.2.1 Subgroup of interest

The primary efficacy will be summarized by the following subgroups to examine the homogeneity of treatment effect based on the FAS:

- Age category (< 65 years, ≥ 65 years)

- MSKCC risk groups: poor (≥ 2 risk factors), intermediate (1risk factors), favorable (0 risk factor)
- IMDC risk groups: poor (> 2 risk factors), intermediate (1-2 risk factors), favorable (0 risk factor)
- Line of therapy (2nd / 3rd):
 - Second-Line therapy: all patients who received only one line of prior antineoplastic therapy before start of the study treatment
 - Third-Line therapy: all patients who received two lines of prior antineoplastic therapies before start of the study treatment

No formal statistical test of hypotheses will be performed for the subgroups, only point estimate of the treatment effect and 95% confidence intervals will be provided (see Sections [2.5.4](#) and [2.7.1](#) for further analysis details). The objective of the efficacy subgroup analysis is to evaluate homogeneity of treatment effect in the above subgroups.

Summary tables will only be performed if at least 20% of patients are present in each subgroup. Some grouping of classes may be considered for some subgroups (e.g. therapy type).

2.3 Patient disposition, demographics and other baseline characteristics

The Full Analysis Set (FAS) will be used for all baseline and demographic summaries and listings unless otherwise specified.

Basic demographic and background data

All demographic and baseline disease characteristics data will be summarized and listed. Categorical data (e.g. gender, age groups: < 65 and ≥ 65 years, race, ethnicity, Karnofsky performance status, MSKCC, IMDC risk group etc.) will be summarized by frequency counts and percentages; the number and percentage of patients with missing data will be provided. Continuous data (e.g. age, weight, height, body mass index etc.) will be summarized by descriptive statistics (N, mean, median, standard deviation, minimum and maximum, 25th and 75th percentiles). BMI (kg/m²) will be calculated as weight[kg] / (height[m]²) using weight at Baseline.

Baseline stratification factors

Not applicable.

Diagnosis and extent of cancer

Summary statistics will be tabulated for diagnosis and extent of cancer. This analysis will include the following: details of tumor histology/cytology, histological grade, stage at initial diagnosis, time since initial diagnosis, stage at time of study entry, presence/absence of target

and non-target lesions, metastatic sites involved. Note: Presence/absence of target and non-target lesions will be based on the data collected on RECIST target/non-target lesion assessment eCRF pages. Presence/absence of metastatic sites will be based on diagnosis page.

Medical history

Medical history and ongoing conditions, including cancer-related conditions and symptoms entered on (e) CRF will be summarized and listed. Separate summaries will be presented for ongoing and historical medical conditions. The summaries will be presented by primary system organ class (SOC) and preferred term (PT). Medical history and current medical conditions will be coded using the Medical Dictionary for Regulatory Activities (MedDRA) terminology. The MedDRA version used for reporting will be specified in the CSR and as a footnote in the applicable tables/listings.

Other

Other data collected at baseline including child bearing potential will be listed.

Patient disposition

The number (%) of treated patients included in the FAS will be presented. The number (%) of patients in the FAS who are still on treatment, who discontinued the study phases and the reason for discontinuation will be presented.

The following summaries will be provided (with % based on the total number of FAS patients):

- Number (%) of patients who are still on-treatment (based on the 'End of Treatment Phase Disposition' page not completed);
- Number (%) of patients who discontinued the study treatment phase (based on the 'End of Treatment Phase Disposition' page)
- Primary reason for study treatment phase discontinuation (based on the 'End of Treatment Phase Disposition' page)
- Number (%) of patients who have entered the post-treatment follow-up (based on the 'End of Treatment Phase Disposition' page);
- Number (%) of patients who have discontinued from the post-treatment follow-up (based on the 'End of Post-treatment phase disposition' page);
- Reasons for discontinuation from the post-treatment follow-up (based on 'End of Post-treatment phase disposition' page);
- Number (%) of patients who have entered the survival follow-up (based on the 'End of Post-treatment phase disposition' page and 'End of Treatment Phase Disposition' page).

Protocol deviations

The number (%) of patients in the FAS with any protocol deviation will be tabulated by deviation category (as specified in the study Study Specification Document). All protocol deviations will be listed.

Analysis sets

The number (%) of patients in each analysis set (defined in [Section 2.2](#)) will be summarized.

2.4 Treatments (study treatment, rescue medication, concomitant therapies, compliance)

2.4.1 Study treatment / compliance

Duration of exposure to pazopanib (expressed in months), actual cumulative dose, dose intensity (DI) and relative dose intensity (RDI) will be summarized. Duration of exposure will be categorized into time intervals; frequency counts and percentages will be presented for the number(%) of patients in each interval. The number (%) of patients who have dose reductions or interruptions, and the reasons, will be summarized.

Patient level listings of all doses administered on treatment along with dose change reasons will be produced.

The safety set will be used for all summaries and listings of study treatment.

Duration of exposure to study treatment

Duration of exposure to study treatment is considered by taking into account the duration of exposure to pazopanib:

Duration of exposure to pazopanib (*months*) =((last date of exposure to pazopanib) – (date of first administration of pazopanib) + 1) / (365.25/12).

The last date of exposure to pazopanib is the latest of the last dates of exposure to pazopanib (see section 2.1.1.)

Summary of duration of exposure of pazopanib in appropriate time units will include categorical summaries (<3 months, 3-<6 months, 6-<12 months, 12-<18 months, \geq 18 months) and continuous summaries (i.e. mean, standard deviation etc.) using appropriate units of time.

Cumulative dose

Cumulative dose of a study treatment is defined as the total dose given during the study treatment exposure and will be summarized.

The **planned cumulative dose** for a study treatment refers to the total planned dose as per the protocol up to the last date of study treatment administration.

The **actual cumulative dose** refers to the total actual dose administered, over the duration for which the patient is on the study treatment as documented in the Dose Administration eCRF.

For patients who did not take any drug the cumulative dose is by definition equal to zero.

For continuous dosing, the actual cumulative dose is the sum of the non-zero doses recorded over the dosing period and the planned cumulative dose is the planned starting dose summed over the same dosing period.

Dose intensity and relative dose intensity

Dose intensity (DI) for patients with non-zero duration of exposure is defined as follows:

DI (mg/day) = Actual Cumulative dose (mg) / Duration of exposure to study treatment (day).

For patients who did not take any drug the DI is by definition equal to zero.

Planned dose intensity (PDI) is defined as follows:

PDI (mg/day) = Planned Cumulative dose (mg) / Duration of exposure (day).

Relative dose intensity (RDI) is defined as follows:

RDI = DI (mg/day) / PDI (mg/day).

DI and RDI will be summarized. RDI will also be summarized by the following categories: $\leq 75\%$, $>75\text{-}90\%$, $>90\text{-}110\%$ and $>110\%$.

Dose reductions, interruptions or permanent discontinuations

The number of patients who have dose reductions or interruptions, and the reasons, will be summarized.

'Dose interrupted' and 'Dose changed' fields from the Dosage Administration CRF pages (DAR) will be used to determine the dose reductions and dose interruptions.

The corresponding fields 'Reason for dose change/dose interrupted' will be used to summarize the reasons.

For the purpose of summarizing interruptions and reasons, in case multiple entries for interruption that are entered on consecutive days with different reasons will be counted as separate interruptions. However, if the reason is the same in this mentioned multiple entries on consecutive days, then it will be counted as one interruption.

Reduction: A dose change where the prescribed dose level is lower than the previous prescribed dose level. Therefore any dose change to correct a dosing error will not be considered a dose reduction. Only dose change is collected in the CRF, number of reductions will be derived programmatically based on the change and the direction of the change.

Missing data: If dose is recorded but regimen is missing or entered as 'none', it is assumed that the study treatment was taken as per-protocol.

2.4.2 Prior, concomitant and post therapies

Prior anti-cancer therapy

The number and percentage of patients who received any prior anti-neoplastic medications, prior anti-neoplastic radiotherapy or prior anti-neoplastic surgery will be summarized. Prior anti-neoplastic medications will be summarized by lowest ATC class and preferred term.

Separate listings will be produced for prior anti-neoplastic medications and surgery.

Anti-neoplastic medications will be coded using the WHO Drug Dictionary (WHO-DD); anti-neoplastic surgery will be coded using MedDRA. Details regarding MedDRA and WHO-DD version will be included in the footnote in the tables/listings.

The above analyses will be performed using the Full Analysis Set.

Post treatment anti-cancer therapy

Anti-neoplastic therapies since discontinuation of study treatment will be listed and summarized by ATC class and preferred term by means of frequency counts and percentages using the Full Analysis Set.

Concomitant medications

Concomitant therapy is defined as all interventions (therapeutic treatments and procedures) other than the study treatment administered to a patient coinciding with the study treatment period. Concomitant therapy include medications (other than study drugs) starting on or after the start date of study treatment or medications starting prior to the start date of study treatment and continuing after the start date of study treatment.

Concomitant medications will be coded using the World Health Organization (WHO) Drug Reference Listing (DRL) dictionary that employs the WHO Anatomical Therapeutic Chemical (ATC) classification system and summarized by lowest ATC class and preferred term using frequency counts and percentages. Surgical and medical procedures will be coded using MedDRA and summarized by SOC and preferred term. These summaries will include:

1. Medications starting on or after the start of study treatment but no later than 30 days after start of last dose of study treatment and
2. Medications starting prior to start of study treatment and continuing after the start of study treatment.

All concomitant therapies will be listed. Any concomitant therapies starting and ending prior to the start of study treatment or starting more than 30 days after the last date of study treatment will be flagged in the listing. The safety set will be used for all concomitant medication tables and listings.

2.5 Analysis of the primary objective

The primary objective of the study is to evaluate the efficacy of pazopanib as assessed by progression-free survival (PFS) in patients with locally recurrent or metastatic RCC with predominantly clear cell component after previous therapy with immune checkpoint inhibitor treatment.

2.5.1 Primary endpoint

The primary endpoint of the study is PFS, defined as the time from the date of start of study treatment to the date of the first documented progression or death due to any cause. For the primary efficacy analysis, PFS will be based on local investigators review of tumor assessments using RECIST v1.1 criteria (see Appendix 2 of the study protocol). The primary analysis will be based on FAS and will include all data observed up-to the cut-off date. If a patient has not progressed or died at the analysis cut-off date, PFS will be censored at the date of the last adequate tumor evaluation date before the cut-off date. PFS events documented after the initiation of new anti-neoplastic therapy (i.e. RECIST v1.1. documented disease progression or

death) will be considered for the primary analysis provided tumor assessments continue after initiation of new cancer therapy (See [Section 2.5.3](#) for additional details regarding censoring rules and determination of date of last adequate tumor assessment). Discontinuation due to disease progression (collected on the 'End of treatment' and 'End of post treatment follow up' disposition pages) without supporting objective evidence satisfying progression criteria per RECIST v1.1 will not be considered disease progression for PFS derivation.

2.5.2 Statistical hypothesis, model, and method of analysis

No formal hypothesis will be tested in the study.

The survival distribution of PFS will be estimated using the Kaplan-Meier method. The results will be plotted graphically. The median, 25th and 75th percentiles of PFS along with 95% confidence intervals will be presented. The survival probabilities at every 2 months up to 12 months, and the associated 95% confidence intervals will be summarized.

The primary efficacy analysis will be performed on the FAS.

2.5.3 Handling of missing values/censoring/discontinuations

In the primary analysis, PFS will be censored at the date of the last adequate tumor assessment if no PFS event (disease progression or death due to any cause) is observed prior to the analysis cut-off date.

PFS events documented after the initiation of new anti-neoplastic therapy (i.e. RECIST v1.1 documented disease progression or death) will be considered for the primary analysis provided tumor assessments continue after initiation of new cancer therapy.

The date of last adequate tumor assessment is the date of the last tumor assessment with overall lesion response of CR, PR or SD before an event or a censoring reason occurred. In this case the last tumor evaluation date at that assessment will be used. If no post-baseline assessments are available (before an event or a censoring reason occurred) then the date of start date of treatment will be used.

In particular, PFS will be censored at the last adequate tumor assessment if one of the following occurs: absence of event; the event occurred after two or more missing tumor assessments. The term "missing adequate tumor assessment" is defined as a tumor assessment (TA) not performed or tumor assessment with overall lesion response of "UNK". The rule to determine number of missing TAs is based on the time interval between the date of last adequate tumor assessment and the date of an event. If the interval is greater than twice the protocol-specified interval between the TAs and 2 times the protocol-allowed time window around assessments, then the number of missing assessments will be 2 or more.

Refer to [Table 2-4](#) for censoring and event date options and outcomes for PFS.

Table 2-4 Outcome and event/censor dates for PFS analysis

Situation	Date	Outcome
No baseline assessment	Date of start of study treatment	Censored
Progression or death at or before next scheduled Assessment	Date of progression (or death)	Progressed

Situation	Date	Outcome
Progression or death after exactly one missing assessment	Date of progression (or death)	Progressed
Progression or death after two or more missing assessments	Date of last adequate assessment prior to missed assessment	Censored
No progression (or death)	Date of last adequate assessment	Censored
Treatment discontinuation due to 'Disease progression' without documented progression, i.e. clinical progression based on investigator claim	Date of last adequate assessment	Censored
New anticancer therapy given prior to protocol defined progression	Ignore the new anticancer therapy and follow situations above	As per above situations
Death before first PD assessment	Date of death	Progressed

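### SAP Table 2-4 censors patients who stop on undocumented clinical progression without condition, contradicting its own death rows and the rest of the plan

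*SAP*

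**What the plan says.** - **SAP 2.5.1.** PFS ends at RECIST progression or at death, whatever its cause. The censoring sentence opens "If a patient has not progressed or died at the analysis cut-off date", so it reaches only patients with neither. An unsupported claim of progression does not itself count as progression.
- **SAP 2.5.3, text.** Two grounds for censoring are named: "absence of event; the event occurred after two or more missing tumor assessments". The second is judged by the gap between the last adequate scan and the event: "If the interval is greater than twice the protocol-specified interval between the TAs and 2 times the protocol-allowed time window around assessments", two or more assessments are taken as missing. Protocol 10.4.3 has the same two grounds and keeps the true date of an event that follows a single missed assessment.
- **SAP Table 2-4, death rows.** "Progression or death at or before next scheduled Assessment" is an event on its date. So is progression or death after exactly one missing assessment. "Death before first PD assessment" is an event on the date of death.
- **SAP Table 2-4, clinical-progression row.** "Treatment discontinuation due to 'Disease progression' without documented progression, i.e. clinical progression based on investigator claim" is censored at the last adequate assessment, with no qualifier. The row after it, on new therapy, does defer to the others: "Ignore the new anticancer therapy and follow situations above".
- **SAP 2.5.4.** Five censoring reasons are listed. None is clinical progression.
- **Protocol Appendix 2, Table 3-2, situation E.** The default is to disregard the claim and apply the other situations. The alternative counts an event at discontinuation. Section 3.2.10 asks that any move away from the default be defined and explained. SAP Section 4 lists no such change.

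**The concern.** Table 2-4 is the summary that a programmer would naturally code for the primary endpoint. For one kind of patient it gives two outcomes and does not say which row wins: a patient who stops on a clinical claim, never has RECIST progression, and dies soon after the last adequate scan.

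If the clinical-progression row is applied as written, that death leaves the analysis although PFS includes death from any cause. Appendix 2, section 4.4 reserves this discontinuation reason for documented symptom deterioration, so the censoring would probably be informative and the median would be too long.

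No other planned PFS analysis would expose the error. SAP 2.5.4 gives supportive analyses as not applicable, the per-protocol analysis was dropped (SAP Section 4), and the subgroup analyses use the same conventions.

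**Working it through.** **1. The window.** Scans are every 8 weeks (56 days) in the first year on treatment, and every 8 weeks in efficacy follow-up, with ±7 days (protocol 7.2.1, Table 7-3). The SAP 2.5.3 limit is 2 × 56 + 2 × 7 = 126 days. A death up to 126 days after the last adequate scan therefore has fewer than two missing assessments.

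**2. One patient, two outcomes.** Stable disease on day 113; stops on a clinical claim on day 130; no RECIST progression; dies on day 165.
- Gap from last adequate scan to death: 165 − 113 = 52 days, inside 126.
- Next scheduled scan: 113 + 56 = day 169, so the death comes before it.
- Death row: event on day 165. Clinical-progression row: censored on day 113.
- Stopping is 130 − 113 = 17 days after the scan, so the 21-day rule in protocol 7.2.1 requires no End of Treatment scan. If prompt imaging on day 130 showed no progression, the clash would remain: event on day 165 or censoring on day 130.

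**3. Does a 2.5.4 reason fit?** The patient has died, so is not ongoing without event. There is no loss to follow-up or consent withdrawal. Both remaining reasons need a gap beyond the limit, and 52 is not above 126. None fits.

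**4. The plan's precision figure.** Inputs from protocol 10.8 and SAP 3.1: N = 100, median 5 months, 12 months' accrual, 6 months' follow-up. Assume exponential PFS and uniform accrual.
- L = ln 2 / 5 = 0.1386
- P(event) = 1 − (e^(−6L) − e^(−18L)) / (12L) = 0.788, so d = 78.8 events
- CI = 5 × exp(±1.96/√78.8) = 4.01 to 6.24, width 2.23, as the table states; half-width 2.23/2 = about 1.1 months

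**5. Size per lost death, if the row is coded literally.**
- *By hand.* The exponential median is proportional to follow-up time over events. Removing one event and keeping follow-up nearly the same gives 5 × 78.8/77.8 = 5.06, or +0.06 month.
- *Simulation with scan schedule.* N = 100, exponential median 5, the accrual above, scans ±7 days, stopping at true failure, death on average 90 days after stopping, 1,500 runs. The share stopping on a claim with no later RECIST progression is assumed. At 2%, the Kaplan-Meier median goes from 5.78 to 5.83 with 1.0 death lost: 0.05/1.0 = 0.05. At 5%, it goes from 5.81 to 5.94 with 2.5 lost: 0.13/2.5 = 0.05.
- *Simulation without scan delay.* 5% of PFS events are assumed to be such deaths and all are lost; 3,000 runs. Events fall from 78.7 to 74.8 and the median rises from 4.97 to 5.25: 0.28/3.9 = 0.07. With the figures rounded (79 to 75 events, 4.95 to 5.25), it is 0.30/4 = 0.075.

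Together: roughly 0.05 to 0.08 month per lost death per 100 patients, or 4% to 7% of the half-width (0.05/1.115 and 0.08/1.115).

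**6. Direction.** If stopping is unrelated to outcome and scans continue, the shift is +0.02 month at 2% and 0.00 at 5%. The upward bias depends on stopping being informative.

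**The case against.** The strongest reply is that the plan already answers the question. SAP 2.5.1 and 2.5.3, the censoring reasons, protocol 10.4.3 and the Appendix 2 default all lead to counting the death. The row can also be read as the table form of the 2.5.1 rule that a claim alone is not progression, covering only patients with no event. This stands as the better reading of the plan as a whole. It does not rescue the row: on that reading it merely repeats the row above it, which has the same date and outcome, and it lacks both that row's mention of death and the next row's deferral. Nothing in the table tells a programmer to read it so.

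The second reply is that few patients will be affected. Protocol 7.2.1 requires prompt imaging when progression is suspected and, with the 21-day exception, a scan at End of Treatment. That stands.

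Several stronger readings are tempting, and the documents do not support them.
- *A 182-day window after year 1* (2 × 84 + 2 × 7). Patients who stop without RECIST progression before LPFV + 1 year are scanned every 8 weeks (protocol 7.1.5.2, 7.2.1), and the primary cut-off follows about six cycles after the last patient starts. The scan-schedule simulation did allow 182 days after year 1, so it may count slightly too many deaths.
- *A shift of several tenths of a month.* That needs 10% to 20% of patients in this group; the documents give no share.
- *Loss of later RECIST progressions.* The row's own condition, no documented progression, may already exclude them.
- *A second conflict for late deaths with no post-baseline scan.* There the 2.5.3 text sets the reference date ("then the date of start date of treatment will be used") and points to censoring. It is a separate and weaker matter, not part of this point.

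**Conclusion.** The point holds as an internal contradiction in the derivation table for the primary endpoint. The clinical-progression row states a rule that the rest of the SAP and the protocol do not support, and no departure is declared.

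A reader might infer that the sponsor intends to censor these deaths, or that the reported median will be biased. The documents support neither: under the reading they favour, the shift is zero and the planned interval of 4.01 to 6.24 months is unaffected. The risk arises only if the row is coded literally. The effect is then about 0.05 to 0.08 month upward per lost death per 100 patients, assuming exponential PFS with a 5-month median and stopping tied to true failure. The number of such deaths is unknown and should be low. The rule that a clinical claim alone is not progression is not challenged.

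This should be fixed, because it concerns the primary endpoint and costs almost nothing.

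**What to change.** In Table 2-4, replace the row's date and outcome with the deferral that the next row already uses: disregard the clinical claim, apply the situations above, and take the outcome from whichever of them fits. A patient with no event is still censored at the last adequate assessment, and an in-window death becomes an event on its date.

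If the sponsor does intend to censor these deaths, SAP Section 4 should say so and why, and 2.5.4 should gain a matching censoring reason.

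Cost: one table row, or a short justification and one added category. No new data and no extra analysis are needed.
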